9.4.2.3 Immunological analyses

For all endpoints relating to immunological assessments, descriptive statistics for the value, change from Baseline, and percentage change from Baseline will be tabulated by dose arm, and time point for the SS. The immunological assessments will include [REDACTED]

[REDACTED] Baseline values from

MG0003 will serve as the Baseline value for MG0007.

For complement where data has been collected post adverse event, individual patient data may be correlated with infusion reaction or hypersensitivity reaction.

9.4.2.4 Anti-drug antibodies analyses

Samples will first be evaluated in the screening assay using a false positivity rate of 5% (reported as negative screen or positive screen), followed by analysis of screened positive samples in the confirmatory assay (which is a drug depletion assay) to confirm the true positivity of the samples (reported as negative immunodepletion or positive immunodepletion). Samples that are confirmed as positive will be evaluated in a titration assay to quantify the ADA level and will be reported as titer (reciprocal dilution factor including minimum required dilution). For ADA-positive immunodepletion samples (or subset of), further characterization for neutralizing ADA potential in vitro will be performed.

The ADA sample status will be summarized by time point for each cycle. Changes from Baseline in sample status in terms of participant ADA classification will be summarized to inform on the incidence and emergence of ADA positivity. Graphical summaries may also be presented. Associations between ADA and PK, PD, efficacy and safety endpoints may be explored if warranted. Full details will be provided in the SAP.

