10.3 Anti-drug antibody and neutralizing antibody (NAb) status

The ADA of rozanolixizumab will be measured using a three-tiered assay approach: screening assay, confirmatory assay and titration assay. Any sample confirmed positive for ADA will be assayed to determine whether there is neutralizing potential.

Evaluation of rozanolixizumab immunogenicity will be performed using data from all evaluable study participants in the SS, defined as all study participants who have an evaluable pretreatment (baseline) sample (negative or positive ADA sample status), and at least 1 evaluable post-Baseline value.

Study participants with an evaluable pretreatment (baseline) sample but without a single evaluable sample taken post-Baseline will be included in the reporting of pre-existing ADA but excluded from all other immunogenicity analyses.

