10.3.1 Data consideration

ADA Sample Status

The ADA sample status will be determined for each pre-treatment (Baseline) and post-treatment (post-Baseline) visit where samples are taken for ADA analysis.

- Sample values that are either ‘negative screen’ or ‘positive screen’ and ‘negative immunodepletion’ will be defined as **ADA negative** if corresponding rozanolixizumab concentrations are equal or below the validated drug tolerance limit of the ADA assay (200µg/mL rozanolixizumab) allowing detection of 100ng/mL ADA
- Sample values that are either ‘negative screen’ or the combination of ‘positive screen’ and ‘negative immuno-depletion’, but with corresponding rozanolixizumab concentrations above the validated drug tolerance limit of the ADA assay, will be defined as ADA inconclusive
- Sample values that are ‘positive screen’ and ‘positive immunodepletion’ will be defined as **ADA positive**
- Samples that could not be tested for ADA status due to inadequate sample volume, mishandling, or errors in sample collection, processing, storage, etc, will be defined as **Missing**.

Neutralizing antibody (NAb) sample status (positive/negative/missing) will be determined for ADA positive samples. Samples that are NAb positive will be evaluated in a titration assay to quantify the NAb level and will be reported as titer.

Definition of ADA Baseline

Baseline for anti-drug antibody (ADA) for MG0007 should be the last measurement prior to receiving the very first rozanolixizumab (RLZ) infusion across all MG studies. Specifically, baseline for ADA is define as:

- MG0003 ADA baseline if participants randomized to RLZ groups in MG0003;
- MG0004 ADA baseline if participants randomized to placebo in MG0003 and enrolled in MG0004 before entering MG0007;
- MG0007 ADA baseline of first study cycle if participants randomized to placebo in MG0003 and enrolled straight into MG0007.

If the ADA sample status for the visit prior to the first dose of RLZ is missing, the last non missing sample will be used.

ADA/NAb Participant Status

The ADA participant status will be classified on study participant and group level as outlined below (Shankar et al. 2014; Rup et al, 2015). A description of how study participants will be categorized for the immunogenicity assessment is provided in [Table 10-1](#).

Individual study participants will be assessed for ADA participant status, composed of 6 categories: ADA negative, inconclusive, and ADA positive, whereby a positive participant’s

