status is determined as originating from a treatment-induced, boosted, reduced or unaffected ADA response.

Study participants who are identified as being treatment-induced or treatment-boosted ADA-positive will be grouped as treatment-emergent (TE)-ADA positive participants. Study participants who are identified as being treatment-reduced or treatment-unaffected ADA-positive will be grouped as non-TE-ADA positive participants. Both TE-ADA positive and non-TE-ADA positive participants will be further classified as NAb negative or NAb positive.

The individual and combined ADA participant categories will be derived and summarized through each scheduled assessment visit (Day 1, Day 22, Day 43, Day 99 for Cycle 1, Day 1 and Day 43 for subsequent cycle, up to the last visit, and EOS visit), unless specified otherwise. Post-Baseline time points where no ADA sample was collected, will be ignored for the categorization.

Table 10-1: Terms and Definitions for ADA Status Evaluation in Study Participant

Classification	Classification Label	Definition
Individual participant categories		
1	Pre-ADA negative – treatment induced ADA negative (ADA-NEG)	Study participants who have an ADA negative sample at Baseline and at all sampling points post-Baseline up to the timepoint of interest.
2	Inconclusive	Study participants who have an ADA positive or negative Baseline sample and some post-Baseline samples are missing or inconclusive, while other post-Baseline samples are ADA negative up to the timepoint of interest.
3	Pre-ADA negative – treatment induced ADA positive (TI-POS)	Study participants who have an ADA negative sample at Baseline and have at least one ADA positive sample at any sampling point post-Baseline up to the timepoint of interest.
4	Pre-ADA positive – treatment boosted ADA positive (TB-POS)	Study participants who have an ADA positive sample at Baseline and at least one ADA positive sample at any sampling point post-Baseline up to the timepoint of interest, with increased titer values compared to Baseline (greater than a predefined fold difference increase from Baseline value which will be defined within the validation of the assay ie MSR of the assay).
5	Pre-ADA positive – treatment reduced ADA positive (TR-POS)	Study participants with an ADA positive sample at Baseline, and ADA negative samples at all sampling points post-Baseline up to the timepoint of interest.

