6	Pre-ADA positive – treatment unaffected ADA positive (TU-POS)	Study participants with an ADA positive sample at Baseline and an ADA positive sample at any sampling point post-Baseline up to the timepoint of interest.

Table 10–1: Terms and Definitions for ADA Status Evaluation in Study Participant

		interest, with titer values of the same magnitude as Baseline (less than a predefined fold difference from the Baseline value which will be defined within the validation of the assay, ie MSR of the assay ¹).
Combined participant categories		
7	Treatment emergent ADA positive (TE-POS)	Includes study participants who are treatment induced ADA positive (category 3) or treatment boosted ADA positive (category 4).
8	Non-treatment emergent ADA positive (Non-TE-POS)	Includes study participants who are treatment reduced ADA positive (category 5) or treatment unaffected ADA positive (category 6).
9	Treatment emergent ADA positive – NAb positive (TE-POS, NAb-POS)	Includes study participants who are treatment emergent positive (category 7) and have at least one NAb positive sample.
10	Treatment emergent ADA positive – NAb negative (TE-POS, NAb-NEG)	Includes study participants who are treatment emergent positive (category 7) and have no NAb positive samples.
11	Non-treatment emergent ADA positive - NAb positive (Non-TE-POS, NAb-POS)	Includes study participants who are non-treatment emergent positive (category 8) and have at least one NAb positive sample.
12	Non-treatment emergent ADA positive - NAb negative (Non-TE-POS, NAb-NEG)	Includes study participants who are non-treatment emergent positive (category 8) and have no NAb positive samples.

Note: if a participant has no baseline ADA, then she/he can't be treated as "Inconclusive".

¹ The fold difference increase from baseline value, ie the minimum significant ratio (MSR=1.36) determined during assay validation, will be reported in the relevant tables, listings and figures. It reflects the fold difference in titer level that considered higher than the assay variation in titer determination.

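### SAP Table 10-1 counts an ADA-positive participant whose neutralising-antibody results are missing as NAb-negative by default

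*Protocol*

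**What the plan says.** Protocol 9.4.2.4 describes NAb testing in one sentence: "For ADA-positive immunodepletion samples (or subset of), further characterization for neutralizing ADA potential in vitro will be performed". It gives no rule for choosing a subset and closes with "Full details will be provided in the SAP".

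The SAP is firmer on testing. Section 10.3 states: "Any sample confirmed positive for ADA will be assayed to determine whether there is neutralizing potential". Section 10.3.1 then sets three sample-level outcomes: "Neutralizing antibody (NAb) sample status (positive/negative/missing) will be determined for ADA positive samples".

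At participant level there are two: "Both TE-ADA positive and non-TE-ADA positive participants will be further classified as NAb negative or NAb positive". Table 10-1 defines the NAb-negative side by what is absent. Category 10: "Includes study participants who are treatment emergent positive (category 7) and have no NAb positive samples". Category 12: "Includes study participants who are non-treatment emergent positive (category 8) and have no NAb positive samples". Categories 9 and 11, the NAb-positive side, need one positive sample.

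For ADA itself the SAP treats gaps differently. Category 2, Inconclusive, begins "Study participants who have an ADA positive or negative Baseline sample and some post-Baseline samples are missing or inconclusive" and applies when the other post-Baseline samples are ADA negative.

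**The concern.** A rule that fills the negative category by absence of a positive result treats no result and a negative result as the same thing. The plan itself foresees missing NAb results, since it lists that status. NAb testing also comes after screening, confirmation and titration, so the causes the SAP names for missing ADA status (low volume, mishandling, storage errors) can apply here too.

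Two things are at stake. The participant-level count of NAb-positive participants may be too low. And the NAb-negative group may contain undetected positives when it is set beside the NAb-positive group on maximum IgG reduction to Day 43 and MG-ADL change at Day 43. If neutralising antibodies weaken the effect, that mixing narrows the visible difference.

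**Working it through.** The documents give no figure on this point, so there is none to reproduce. The check is mainly of the text.

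**1. Follow one participant through the rules.** Take a participant who is ADA-negative at Baseline and has one ADA-positive sample afterwards, with its NAb result missing.
- Category 7 (treatment-emergent ADA positive): yes.
- Category 9 (needs at least one NAb-positive sample): no.
- Category 10 (needs no NAb-positive sample): yes.
- Category 2: not applicable. It concerns ADA status, and this participant has a positive ADA sample.

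The participant is reported as treatment-emergent ADA positive, NAb-negative, without any NAb result. The same steps lead a non-treatment-emergent participant to category 12.

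**2. Compare with the neighbouring rules in the SAP.**
- ADA at participant level: missing or inconclusive samples among negatives give Inconclusive.
- By-visit NAb table (10.3.2): missing is its own level, and the denominator is participants with a non-missing result.
- Pre-existing ADA and NAb prevalence (10.3.2): missing samples are left out of the denominator.
- Participant-level NAb (Table 10-1): missing becomes negative.

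Only the last converts missing to negative.

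**3. Direction.** A missing result can move a true NAb-positive participant into NAb-negative. It cannot do the reverse. No assumption is needed for the sign.

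**4. Size, as illustration only.** Let p be the true NAb-positive share among ADA-positive participants and u the share with no NAb result, unrelated to true status. The documents give neither. Treat each participant as wholly tested or wholly untested.
- Reported positive share = p(1 − u)
- Hidden positives within the NAb-negative group = up / (1 − p + up)

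| p | u | Reported positive | Hidden positives in NAb-negative group |
|---|---|---|---|
| 30% | 5% | 0.30 × 0.95 = 28.5% | 0.015 / 0.715 = 2.1% |
| 60% | 5% | 0.60 × 0.95 = 57% | 0.030 / 0.430 = 7.0% |
| 50% | 10% | 0.50 × 0.90 = 45% | 0.050 / 0.550 = 9.1% |
| 50% | 20% | 0.50 × 0.80 = 40% | 0.100 / 0.600 = 16.7% |

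**5. Repeated sampling shrinks this.** One NAb-positive sample is enough for NAb-positive status, so a true positive is hidden only if all of that participant's NAb-positive samples lack a result. With three such samples and an assumed independent 10% loss per sample, the chance is 0.1³ = 0.1%. The table above therefore fits participants with a single ADA-positive sample. One such group is category 5 (treatment-reduced), whose only ADA-positive sample is the Baseline one.

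**6. Denominator.** Moving untested participants to a separate level leaves the number of NAb-positive participants unchanged. If all ADA-positive participants stay in the denominator, the reported share is still p(1 − u). With evaluable participants only, it becomes p(1 − u) / (1 − u) = p under the same assumptions.

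**The case against.** A reader might infer from the protocol's subset wording that participants will be left untested by design and then reported as NAb-negative. The documents do not support that. The protocol leaves full details to the SAP, and SAP 10.3 sends every confirmed ADA-positive sample to the NAb assay. Under the current plan the route is missing results, not planned omission. Large values of u would arise only if the subset option were used despite the SAP.

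It can also be said that the missing results are not concealed. The by-visit table shows them, the prevalence table excludes them, and the by-subject listings give NAb status and titre at each timepoint. ADA is among the other objectives, all analyses are descriptive, and the adverse-event tables by ADA status use categories 1, 2, 7 and 8, which this does not touch. Repeated sampling makes a hidden positive less likely still.

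All of that stands, and it limits the size. It does not change the classification rule: as written, categories 10 and 12 accept a participant with no valid NAb result, and the participant-level outputs do not show how many there are.

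**Conclusion.** The point holds as a defect in a stated definition. Following Table 10-1 exactly, an ADA-positive participant with no valid NAb result is counted as NAb-negative, which is inconsistent with how the SAP treats missing ADA results and with its other NAb denominators.

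The error runs one way, towards too few NAb-positive participants. Its size cannot be derived from the documents and is probably small given SAP 10.3. The percentages above rest on assumed p and u, on missingness unrelated to true status, and on all-or-nothing testing.

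The affected outputs are the participant-status table, the IgG and MG-ADL table, the ADA titre box plots and the MG-ADL time courses that split by categories 9 to 12, and the IgG spaghetti plots for categories 9 and 10. A general claim that NAb reporting is biased would go too far, because the sample-level and prevalence tables handle missing results properly.

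Separately, protocol 9.4.2.4 and SAP 10.3 differ on which samples are tested. SAP section 1 says changes from the protocol are documented in section 3.9, and that section does not list this one.

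**What to change.** In SAP Table 10-1:
- Define categories 10 and 12 by valid negative results. The minimum is at least one valid NAb result and none positive. The stricter form, parallel to ADA category 2, is that every ADA-positive sample up to the timepoint is NAb-negative.
- Add a NAb not-evaluable or inconclusive level in both the treatment-emergent and the non-treatment-emergent ADA-positive groups.

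In SAP 10.3.2, show the count at that level, keep it out of the NAb-negative columns and panels, and base NAb percentages on participants with evaluable NAb status.

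State the choice between the two forms in advance. Under the stricter form one missing result among several negatives makes a participant inconclusive, while one positive among several missing still counts as positive. With an evaluable-only denominator that can push the positive share up, and the inconclusive group can grow over many cycles. The minimum form closes the gap for participants with no result at all and loses fewer participants.

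Reconcile the testing rule by recording in SAP 3.9 that all confirmed ADA-positive samples are assayed. A protocol amendment is not needed for this alone.

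The cost is SAP wording, two extra rows in existing tables, respecified category lists in 10.3.2, and a slightly smaller NAb-negative group. No new data are collected.

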9.5 Handling of protocol deviations

Important protocol deviations are identified as part of the data cleaning process in the Data Cleaning Plan (DCP). Ongoing data cleaning meetings will be held throughout the duration of the study. Objectives of these meetings include to review and update (if necessary) the important protocol deviations in the DCP. Furthermore, overall trends in protocol deviations will be discussed at the Data Evaluation Meeting. Through this ongoing data cleaning and evaluation process, all decisions regarding important protocol deviations are made on an ongoing basis.

9.6 Handling of dropouts or missing data

All imputation of missing or partial dates for safety assessments, as well as handling missing efficacy data (where applicable), will be detailed in the SAP.

9.7 Planned interim analysis and data monitoring

No formal interim analysis is planned for this study.

An Independent Data Monitoring Committee (IDMC) will be established. The IDMC will oversee the safety of the study by reviewing safety and efficacy data at periodic data reviews to assess the benefit-risk of rozanolixizumab. The objectives and procedures for the IDMC will be detailed in the IDMC Charter.

In addition, based on data cutoffs, safety and efficacy data for submission purposes will be summarized.

9.8 Determination of sample size

No formal sample size calculation can be performed. All eligible study participants from MG0003, and MG0004 will be invited to participate in MG0007. It will be assumed that approximately 200 study participants will be enrolled into MG0007.

The number of 200 study participants is assuming a drop-out rate from the lead-in study of approximately 15% (including participants who opt not to continue in MG0007).

10 SUPPORTING DOCUMENTATION AND OPERATIONAL CONSIDERATIONS

10.1 Appendix 1: Regulatory, ethical, and study oversight considerations

10.1.1 Regulatory and ethical considerations

The study will be conducted under the auspices of an IRB/IEC, as defined in local regulations, ICH-GCP, and in accordance with the ethical principles that have their origin in the Declaration of Helsinki.

The Investigator/UCB will ensure that an appropriately constituted IRB/IEC that complies with the requirements of the current ICH-GCP version or applicable country-specific regulations will be responsible for the initial and continuing review and approval of the clinical study. Prior to initiation of the study, the Investigator/UCB will forward copies of the protocol, ICF, IB, Investigator's curriculum vitae (if applicable), advertisement (if applicable), and all other participant-related documents to be used for the study to the IRB/IEC for its review and approval.

Before initiating a study, the Investigator will have written and dated full approval from the responsible IRB/IEC for the protocol.

The Investigator will also promptly report to the IRB/IEC all changes in the study, all unanticipated problems involving risks to participants or others, and any protocol deviations, to eliminate immediate hazards to participants.

The Investigator will not make any changes in the study or study conduct without IRB/IEC approval, except where necessary to eliminate apparent immediate hazards to the participants. For minor changes to a previously approved protocol during the period covered by the original approval, it may be possible for the Investigator to obtain an expedited review by the IRB/IEC as allowed.

As part of the IRB/IEC requirements for continuing review of approved studies, the Investigator will be responsible for submitting periodic progress reports to the IRB/IEC (based on IRB/IEC requirements), at intervals appropriate to the degree of participant risk involved, but no less than once per year. The Investigator should provide a final report to the IRB/IEC following study completion.

UCB (or its representative) will communicate safety information to the appropriate regulatory authorities and all active investigators in accordance with applicable regulatory requirements. The appropriate IRB/IEC will also be informed by the Investigator or the Sponsor, as specified by the applicable regulatory requirements in each concerned country. Where applicable, Investigators are to provide the Sponsor (or its representative) with evidence of such IRB/IEC notification.

10.1.2 Financial disclosure

Insurance coverage will be handled according to local requirements.

Finance and insurance are addressed in the Investigator and/or CRO agreements, as applicable.

10.1.3 Informed consent process

Participant's informed consent must be obtained and documented in accordance with local regulations, ICH-GCP requirements, and the ethical principles that have their origin in the principles of the Declaration of Helsinki.

Prior to obtaining informed consent, information should be given in a language and at a level of complexity understandable to the participant in both oral and written form by the Investigator (or designee). Each participant will have the opportunity to discuss the study and its alternatives with the Investigator.

Prior to participation in the study, the Informed Consent form should be signed and personally dated by the participant, or his/her legal representative, and by the person who conducted the informed consent discussion (Investigator or designee). The participant or his/her legal representative must receive a copy of the signed and dated Informed Consent form. As part of the consent process, each participant must consent to direct access to his/her medical records for study-related monitoring, auditing, IRB/IEC review, and regulatory inspection. For local regulations, see Appendix 8 (Section 10.8).

If the Informed Consent form is amended during the study, the Investigator (or the Sponsor, if applicable) must follow all applicable regulatory requirements pertaining to the approval of the amended Informed Consent form by the IRB/IEC and use of the amended form.

All studies conducted at centers in the United States must include the use of a Health Insurance Portability and Accountability Act Authorization form.

The participant may withdraw his/her consent to participate in the study at any time. A participant is considered as enrolled in the study when he/she has signed the Informed Consent form. A CRF must not be started, nor may any study specific procedure be performed for a given participant, without having obtained his/her written consent to participate in the study.

